3.5. Criteria for Evaluation

Assessments:

- Baseline (at 1st administration of abatacept IV).- the baseline data can be collected at abatacept IV treatment initiation or retrospectively within maximum 3 months following the first administration:
 - Socio-demographics (age, sex, employment status)
 - Disease history & characteristics
 - Prior RA treatments (biologic and conventional DMARDs, other concomitant medication)
- Prospectively, inclusive of baseline (as defined before):
 - Clinical outcomes: DAS28 and its individual components (SJC, TJC, CRP/ESR), CDAI, SDAI³⁴, HAQ-DI, Physician's global assessment
 - Patient-reported outcomes: Patient Global Assessment, Patient satisfaction, Pain (see Appendix)
 - Abatacept dosage and frequency of administration (IV or SC formulation)
 - Reasons and subsequent RA treatment with conventional/biologic DMARDs if abatacept treatment was discontinued
 - Reason for change in the route of administration of abatacept (from IV to SC)
 - Other concomitant medication for RA (doses, frequency)
 - Adverse Drug Reaction

3.6. Discussion of Biases and Study Limitations

3.6.1. Rheumatologist Selection Bias

Two potential rheumatologist selection biases can be anticipated: (1) participation in the study is on a voluntary basis, (2) rheumatologists "interested" in the study could be preferentially those having in their practice a more significant number of patients corresponding to the target population.

A minimum 10% participation rate is expected (as not all centers on the general list of centers are treating patients with biologics and the list of centers that prescribe biologics cannot be identified from the general list of centers before mailing). However, as detailed above (see [section 3.2.1 Sampling Plan](#)), the data of the rheumatologist sample will be compared to the local rheumatologist population to determine the degree to which generalizability of study samples (both rheumatologists and patients) may be established. The findings as well as the assessment of the potential sources/direction of biases introduced by non-random samples will be reported. The demographics of study respondents vs. non-respondents will be also assessed.

3.6.2. Patient Selection Bias

To prevent rheumatologists from selecting "particular" patients, they will be asked to select the first series of consecutive patients (up to 10 for each treatment line of abatacept) fulfilling inclusion criteria and visiting over an accrual period of no more than 2 years. Some rheumatologists are likely not to adhere strictly to this requirement. However, if the reason is lack of time or oversight, or any reason independent of the evaluation criteria, it will not involve a selection bias.

4. DATABASE METHODOLOGY

4.1. Variable Definitions

4.1.1. Description of derived variables – derived clinical outcomes

Detailed definitions of the following derived efficacy criteria are provided in [Appendix 1](#) (see Appendix 1):

- Disease Activity Score 28 (DAS28) based on CRP (DAS28-CRP) or ESR (DAS28-ESR)
- EULAR criteria based on DAS28 (non/moderate responders versus good responders, or non-responders versus moderate/good responders)³⁵
- EULAR criteria based on DAS28:
 - Low Disease Activity State (LDAS) ($DAS28 \leq 3.2$)
 - Remission State ($DAS28 < 2.6$)
- Health Assessment Questionnaire-Disability Index

The derived clinical outcomes will be used as calculated in Appendix 1 (see Appendix 1) but also according to the following definitions (see [Appendix 2](#)³⁶). The Statistical Analysis Plan (to be developed separately later) will give more detail.

1. **Response:** expressed as % of patients achieving EULAR response criteria at each time point;
2. **Status:** expressed as % of patients achieving LDAS, remission at each time point;

4.2. Statistical Analysis plan

All the questionnaire parameters and evaluation criteria (see [section 3.5](#)) will be summarized using descriptive statistics in addition to statistical modelling if needed. Specifically, (1) the sample size, mean, standard deviation, minimum, median, mode, maximum, 95% CI and the number of missing data will be provided for continuous variables; (2) the frequency and percentage by modality, 95% CI and number of missing data will be provided for discrete variables; and (3) the distribution and median of time-to-event data will be analyzed using Kaplan-Meier product limit estimator. The 95 % CIs of the estimates will also be presented. A detailed statistical plan will be developed and approved before database lock.

Data from different countries may be pooled if appropriate, including data from registries.

The analysis will be performed for each participating country. Data from different countries may be pooled if appropriate.

The analysis will be performed separately depending on treatment line of abatacept.

More specifically, the following analysis will be performed:

Primary Analysis:

- The retention rate of RA patients treated with abatacept over 24 months in routine clinical practices will be estimated for each country separately and pooled (if appropriate), depending on treatment line of abatacept
- A change of abatacept route of administration from IV to SC during the follow up period will be not considered as a discontinuation of treatment, but as a treatment modification.

Secondary Analysis:

Information of Participating Centers:

- Descriptive analysis of the participating physicians and assessment of the representativeness with national statistics will be performed. Physicians from the different datasets (respondents accepting participation, respondents refusing participation, non respondents – active and inactive physicians) will be compared to assess the generalizability of the results.

Determinants of Treatment Discontinuation:

- The major determinants of treatment discontinuation of RA patients treated with abatacept in this study will be identified and summarized.
- The retention rate will be estimated for each determinant. The corresponding 95% CI will also be provided.
- The distribution and median of time-to-discontinuation of abatacept therapy for each major determinant of treatment discontinuation will be estimated using Kaplan-Meier method. The corresponding 95% CI will also be provided. In case of missing data at 24 months, the last data point available will be used for this analysis.

Patient Reported Outcomes:

- The patient reported outcomes, such as patient satisfaction, pain, patient's global assessment, etc., of RA patients treated with abatacept in this study will be summarized.
- Relationship between patient reported outcomes, and the derived clinical outcomes as well as the prior RA experience will be estimated.

Treatment Experience/Outcomes after Switching:

- The treatment experience/outcomes (choice of therapy, dose, duration) after switching to a biologic or conventional DMARD for patients who discontinue abatacept therapy will be summarized.

Exploratory Analysis:

Description of potential changes in patient characteristics and in treatment pattern over time in clinical practice in patients treated with abatacept as second or further biologics DMARDs, enrolled during the period 2008-2010 and in patients enrolled during the period 2011-2013 in Europe (Germany, Italy, Austria, The Netherlands, Greece)

- Relationship between abatacept discontinuation and the derived clinical outcomes and the prior RA experience will be investigated.
- Cox proportional hazard regression model will be used to identify factors which contribute to patient discontinuation. The analysis will be conducted at 6 and 12 months and results will be compared to analysis results at 24 months.
 - The distribution of time-to-discontinuation estimated in subgroups of patients based on derived clinical outcomes and prior RA treatment experiences (e.g., patients with incomplete response to 1 or 2 or 3 previous TNF blocking agents) will be compared using a log-rank test at a 95% significance level.
 - Decision-tree method will be utilized to explore the combinations of criteria that can possibly explain the retention at two years.

Description of switch from abatacept IV to abatacept SC including reasons for changing route of administration.

Description of treatment experience/outcomes after switching from abatacept IV to abatacept SC.

Reporting of Interim Analysis

- Interim analysis may be conducted during the follow-up period (e.g. after LPFV for the description of patient population and 6 months and 1 year following LPFV for the preliminary analysis of primary criteria).
- Each interim statistical analysis will be performed depending on treatment line of abatacept.

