2.2. Secondary Objectives

1. To identify the major determinants (including prior RA treatment experience with biologics and clinical outcomes, such as DAS28, HAQ-DI, CDAI, SDAI, and their derived criteria) of treatment discontinuation of RA patients treated with abatacept in this study.
2. To estimate the distribution of time-to-discontinuation of abatacept therapy for each major determinant of treatment discontinuation, overall, depending on the treatment line

3. To estimate the association of prior RA treatment experience and clinical outcomes during the treatment course with patient reported outcomes (Patient satisfaction, Pain, Patient's Global Assessment).
4. To summarize the treatment experience and outcomes after switching to a biologic or conventional DMARD for patients who discontinue abatacept therapy.

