Response criteria (EULAR criteria based on DAS28-CRP): Non and moderate responders versus good responders, or non responders versus moderate and good responders

EULAR criteria for Response to treatment (Fransen et al. Clin Exp Rheumatol 2005; 23 (suppl. 39): S93-S99): ³⁶

	Improvement in DAS28 at evaluation time compared to baseline measurement (absolute difference)		
DAS28 at evaluation time point	1.2 < difference	0.6 < difference ≤ 1.2	difference ≤ 0.6
score ≤ 3.2	good responder	moderate responder	non-responder
3.2 < score ≤ 5.1	moderate responder	moderate responder	non-responder
5.1 < score	moderate responder	non-responder	non-responder

- **Status** : Low Disease Activity State (LDAS) (DAS28-CRP ≤ 3.2); Remission State (DAS28-CRP < 2.6)

- Joint Assessments

All joint counts will be performed by a trained clinical assessor with at least one year of experience in performing examinations in clinical trials. Every effort should be made to ensure the same clinical assessor complete the swollen and tender joint counts for each subject. Visits requiring joint assessment should be scheduled with the availability of the clinical assessor taken into account. If the same clinical assessor is unable to complete the joint assessments, then a qualified individual (trained by the original clinical assessor), with overlapping experience may perform the evaluation. Documentation of training and who performed the joint assessments is to be recorded in the source notes. The joint assessor will also be recorded on the appropriate page of the CRF.

- Subject Global Assessment of Disease Activity

Subject global assessment of disease activity (as part of the DAS28-CRP evaluation) is required at each visits until the end of the study. Subject global assessment of disease activity is to be completed using the visual analog scale represented in [Appendix 1](#). The appropriate page of the CRF should be used as the source document for these measurements and must be completed by the subject. Subjects should complete each assessment without reference to the previous assessment(s). The same ten-centimeter ruler should be used for each assessment.

- Physician Global Assessment of Disease Activity

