Physician global assessment of disease activity is required at each visit until the end of the study). Physician Global Assessment pages may only be completed by a MD. Physician global assessment of disease activity is to be completed using the visual analog scale represented in [Appendix 1](#). The appropriate page of the CRF should be used as the source document for these measurements and must be completed by the physician, without reference to the previous assessment(s). The same ten-centimeter ruler should be used for each assessment.

- Evaluation of HAQ Disability Index

The scoring conventions for this study are based on the Standard Disability Index of HAQ using the 20 response items. The Standard Disability Index (HAQ-DI) takes into account the patient's use of aids or devices or assistance in the scoring algorithm for a disability category. For each of the eight disability categories there is an AIDS OR DEVICES companion variable(s) that is used to record the type of assistance, if any, a patient uses for his/her usual activities. If either aids/devices and/or assistance from another person are checked for a disability category, the score for this category is set to 2 (much difficulty), if the original score is 0 (no difficulty) or 1 (some difficulty). The HAQ-DI is then calculated by summing the adjusted categories scores and dividing by the number of categories answered

SDAI, CDAI:

Aletaha D, Smolen JS.

The Simplified Disease Activity Index (SDAI) and Clinical Disease Activity Index (CDAI) to monitor patients in standard clinical care.

Best Pract Res Clin Rheumatol. 2007 Aug;21(4):663-75)³⁵

Table 1. Disease activity indices: calculation and cutpoints of disease activity categories.

Index	Formula	Cutpoints
DAS-28	$0.56 \times \sqrt{(TJC28)} + 0.28 \times \sqrt{(SJC28)} + 0.70 \times \log_{\text{nat}}(\text{ESR}) + 0.014 \times \text{GH}$	<2.6/<3.2/<5.1*
SDAI	SJC28 + TJC28 + PGA + EGA + CRP	≤3.3/≤11/≤26
CDAI	SJC28 + TJC28 + PGA + EGA	≤2.8/≤10/≤22

Abbreviations: DAS: Disease Activity Score; DAS-28: DAS based on a 28 joint count; CRP, C-reactive protein; EGA, evaluator global assessment of disease activity; ESR, erythrocyte sedimentation rate; GH, global health; PGA, patient global assessment of disease activity; SJC, swollen joint count; TJC, tender joint count.

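### Patient's Global Assessment is to be related to DAS28-based outcomes (and, on one reading, CDAI and SDAI) that contain it, so part of that association is arithmetic

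*Protocol*

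**What the plan says.** Secondary objective 3 (protocol section 2.2) sets out to associate prior RA treatment and "clinical outcomes during the treatment course with patient reported outcomes (Patient satisfaction, Pain, Patient's Global Assessment"). Section 4.2 turns this into an analysis: "Relationship between patient reported outcomes, and the derived clinical outcomes as well as the prior RA experience will be estimated". It makes no exception for PGA.

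Section 3.5 puts the variables on two sides. One side is "Clinical outcomes: DAS28 and its individual components (SJC, TJC, CRP/ESR), CDAI, SDAI", together with HAQ-DI and the physician's global assessment. The other is "Patient-reported outcomes: Patient Global Assessment, Patient satisfaction, Pain".

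Section 4.1.1 lists the derived clinical outcomes: "Disease Activity Score 28 (DAS28) based on CRP (DAS28-CRP) or ESR (DAS28-ESR"), the EULAR response, low disease activity and remission criteria based on DAS28, and HAQ-DI. It says they are used as calculated in Appendix 1. CDAI and SDAI are not on that list. They enter through the wider term clinical outcomes, as used in objective 1 of section 2.2 and in section 3.5.

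Appendix 1 gives the formulas. Both DAS28 versions include 0.014 times the patient's VAS in mm. CDAI is "SJC28 + TJC28 + PGA + EGA", and SDAI adds CRP, with PGA in cm. Appendix 1 also describes the patient's rating as "Subject global assessment of disease activity (as part of the DAS28-CRP evaluation"), so the DAS28 term and the patient-reported outcome are the same measurement.

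**The concern.** When one variable is an additive term of another, the two correlate even if the first is unrelated to everything else in the sum. A reader of objective 3 wants to know whether joint counts, inflammation and physician-assessed activity go with how patients rate their disease. The correlation of PGA with full DAS28 mixes that relation with a fixed contribution from PGA itself, and the result alone does not separate the two. The reported association would be larger than the relation of PGA to the rest of the index.

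**Working it through.** The protocol states no figure for this analysis, so there is none to reproduce.

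**From the protocol's formulas alone**

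- Largest PGA contribution to DAS28: 0.014 × 100 mm = 1.4 points.
- PGA change that alone moves DAS28 past the 0.6 cut-off of the EULAR response table in Appendix 1: 0.6 / 0.014 = 42.9 mm. For the 1.2 cut-off: 1.2 / 0.014 = 85.7 mm.
- The lowest categories are CDAI ≤ 2.8 and SDAI ≤ 3.3, and the other terms cannot be negative. PGA above 2.8 cm therefore rules out the lowest CDAI category by itself, and PGA above 3.3 cm the lowest SDAI category.

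**Built-in correlation when PGA is independent of every other component**

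Let w be the weight of PGA (0.014 per mm in DAS28, 1 per cm in CDAI and SDAI), s the SD of PGA and R the SD of the rest of the index. For values from the same visit:

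r = w·s / √((w·s)² + R²)

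The weights come from Appendix 1. The SDs are assumptions, shown over a range.

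| DAS28 | R = 0.8 | R = 1.0 | R = 1.3 |
|---|---|---|---|
| s = 20 mm | 0.330 | 0.270 | 0.211 |
| s = 25 mm | 0.401 | 0.330 | 0.260 |
| s = 30 mm | 0.465 | 0.387 | 0.307 |

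| CDAI or SDAI | R = 6 | R = 9 | R = 12 |
|---|---|---|---|
| s = 2.0 cm | 0.316 | 0.217 | 0.164 |
| s = 2.5 cm | 0.385 | 0.268 | 0.204 |
| s = 3.0 cm | 0.447 | 0.316 | 0.243 |

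For example, with s = 25 mm and R = 1.0: w·s = 0.35, and 0.35 / √(0.1225 + 1) = 0.330. With the PGA term removed, the built-in part is zero by construction.

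**When a true relation exists**

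Let ρ be the correlation of PGA with the rest of the index. The correlation with the full index is

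(w·s + ρR) / √((w·s)² + R² + 2ρ·w·s·R)

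| ρ | Full DAS28 (s = 25 mm, R = 1.0) | Full CDAI or SDAI (s = 2.5 cm, R = 9) |
|---|---|---|
| 0 | 0.330 | 0.268 |
| 0.2 | 0.489 | 0.438 |
| 0.4 | 0.633 | 0.595 |
| 0.6 | 0.765 | 0.739 |

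Under these assumptions, a correlation of 0.4 with the PGA-free part would be reported as about 0.63 with DAS28.

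**The case against.** The strongest reply is that the protocol fixes no model. Section 4.2 says only that a relationship will be estimated, and the choice of predictors for each outcome is ordinary content for the separate analysis plan, which is not at hand. The PGA-free variables are already in scope: joint counts, CRP or ESR, HAQ-DI and the physician's global assessment. A sound analysis of PGA is therefore possible under the present text. Timing is not fixed either. If earlier clinical values were related to later PGA, the overlap would act only through the correlation of PGA with itself across visits, and the figures above would shrink.

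Much of this stands, and it limits the point. It does not remove it. The protocol names PGA as an outcome, relates it to the derived clinical outcomes without exception, and says those outcomes are used as calculated in Appendix 1. An analysis plan that followed this text would carry the overlap. Of the derived outcomes in section 4.1.1, only HAQ-DI is free of PGA.

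The objection that CDAI and SDAI are not in the section 4.1.1 list is also right. They are affected only if clinical outcomes in objective 3 is read as in objective 1 and section 3.5.

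**Conclusion.** The point holds in a limited form. It concerns one of three patient-reported outcomes in one of four secondary objectives, and only its pairing with DAS28, the categories derived from DAS28 and, on the wider reading, CDAI and SDAI. There the association is inflated. The built-in same-visit correlation is 0.211 to 0.465 for DAS28 and 0.164 to 0.447 for CDAI or SDAI, under the assumed SDs and with PGA independent of the other components. The overlap itself follows from the protocol's formulas. Its size cannot be fixed from the document.

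A reader might infer more than this:

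- **That PGA is being correlated with itself.** It is so only in part; the other components make up the rest of each index.
- **That objective 3 is uninterpretable.** Satisfaction and pain are not terms of these indices. HAQ-DI, the physician's global assessment, joint counts, CRP or ESR and prior RA treatment do not contain PGA. An inflated correlation can also be read beside the component results.
- **That the overlap will yield a false significant result.** Section 4.2 plans no significance test for this relationship.

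The primary objective, retention, is not touched.

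**What to change.** Add one sentence to the patient-reported outcomes part of section 4.2. For the PGA outcome, the association is to be estimated with the separately collected components (tender and swollen joint counts, CRP or ESR, physician's global assessment, HAQ-DI) or with the index without its PGA term. A PGA-free index should be used as a continuous score, because the category cut-offs in Appendix 1 belong to the full index.

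PGA by full DAS28, CDAI or SDAI, or by EULAR response, low disease activity and remission, can still be reported descriptively with a note that the index contains PGA. Barring those summaries would lose the protocol's own response and status definitions for no gain. Satisfaction and pain can be analysed against the full indices as planned.

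The cost is one extra derived variable and a smaller reported association. No new data are needed, since section 3.5 already collects every component.

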 - Derived clinical outcomes: DAS28 derived criteria : EULAR response, LDAS (DAS 28 \leq 3.2), remission (DAS28 $<$ 2.6)
 - DAS 28 (DAS28) based on CRP (DAS28-CRP) or ESR (DAS28-ESR)
 - HAQ-DI derived criteria: HAQ response (change HAQ-DI \geq 0.3)
 - Response/status at each time point, onset of action, durability

Statistical analyses

The analysis will be performed for each participating country. Data from different countries may be pooled if appropriate, depending on treatment line of abatacept.

Descriptive analyses:

- Sample size, mean, standard deviation, minimum, median, mode, maximum, 95% CI and the number of missing data for continuous variables
- Frequency and percentage by modality, 95% CI and number of missing data for discrete variables
- Distribution and median of time-to-event data will be analyzed using Kaplan-Meier product limit estimator

Primary Analysis:

The retention rate of RA patients treated with abatacept (regardless of route of administration) over 24 months in routine clinical practices will be estimated for each country separately and pooled (if appropriate), depending on treatment line of abatacept.

Secondary Analysis:**Information of Participating Centres:**

- Descriptive analysis of the participating physicians and assessment of the representativeness with national statistics will be performed.

Determinants of Treatment Discontinuation:

- The major determinants of treatment discontinuation of RA patients treated with abatacept (regardless of route of administration) in this study will be identified and summarized.
- The retention rate will be estimated for each determinant with corresponding 95% CIs
- The distribution and median of time-to-discontinuation of abatacept therapy for each major determinant of treatment discontinuation will be estimated using Kaplan-Meier method with corresponding 95% CIs.

Patient Reported Outcomes:

- The patient reported outcomes, such as patient satisfaction, pain, patient's global assessment, etc. of RA patients treated with abatacept in this study will be summarized.

Treatment Experience/Outcomes after Switching:

- The treatment experience/outcomes after switching to a biologic or conventional DMARD for patients who discontinue abatacept therapy will be summarized.

Exploratory Analysis:

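### As written, Section 4.2 permits a guarantee-time comparison: time-to-discontinuation is compared across subgroups that include on-treatment response, with no landmark or time-dependent handling

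*Protocol*

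**What the plan says.** Under Exploratory Analysis, Section 4.2 states: "The distribution of time-to-discontinuation estimated in subgroups of patients based on derived clinical outcomes and prior RA treatment experiences", with prior TNF-blocker failures as its example, "will be compared using a log-rank test at a 95% significance level". The same list says a "Cox proportional hazard regression model will be used to identify factors which contribute to patient discontinuation", run at 6, 12 and 24 months, and adds a decision tree for two-year retention.

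Section 4.1.1 defines response as "expressed as % of patients achieving EULAR response criteria at each time point" and status as "expressed as % of patients achieving LDAS, remission at each time point". The Synopsis lists "Response/status at each time point, onset of action, durability" among the derived outcomes. Appendix 1 defines EULAR response by the fall in DAS28 from baseline to the evaluation visit.

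Secondary objective 1 (Section 2.2) counts among the candidate determinants "clinical outcomes, such as DAS28, HAQ-DI, CDAI, SDAI, and their derived criteria". Section 1.3 wants outcomes both at baseline and during the study linked to retention. The secondary analyses in Section 4.2 then give a retention rate and a Kaplan-Meier curve for each determinant. Section 4.5.1 keeps every recruited patient except those with sex or age missing.

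For the log-rank comparison the protocol does not state the time origin, when response is classified, or how patients who stop before classification are grouped. It names no landmark and no time-dependent covariate. The 6- and 12-month Cox analyses are not described as landmarks.

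**The concern.** EULAR response cannot be known at first infusion. A patient classed as a responder at month 6 was necessarily still on abatacept then. A patient who stopped at month 2 could not enter that group and, in a data set of all recruited patients, tends to be placed with the non-responders. Counted from first infusion, the responder curve is then protected from events up to classification while the other curve absorbs all the early stops. The curves separate even if response has no bearing on later discontinuation.

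This bears on secondary objectives 1 and 2, which are to identify determinants of discontinuation and describe time-to-discontinuation by determinant. An on-treatment outcome could be reported as a strong determinant on the strength of how the groups were formed.

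**Working it through.** **The plan's own figure.** Section 4.3.1 expects 60% ± 5% with 370 patients. Half-width = 1.96 × √(0.60 × 0.40 / 370) = 1.96 × 0.0255 = 0.050, so the figure is reproduced. The protocol gives no power or event count for the log-rank comparisons.

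**Inputs from the protocol.** n = 370 and 24-month retention of 60% (Section 4.3.1); visits about every 3 months and 2 years of follow-up (Section 3.1).

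**Assumptions.** Exponential discontinuation; response independent of discontinuation, so the true hazard ratio is 1; chance q of first response at each visit of 0.05, 0.10 or 0.20, because the protocol gives no response rate; log-rank test read as two-sided 5%.

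**Month-6 arithmetic.** S(6) = 0.60^(6/24) = 0.88, so 12% have stopped. Responders' 24-month retention = 0.60 / 0.88 = 68%. If a fraction r of those still treated respond and early stoppers count as non-responders, the other group retains 0.60(1 − r) / [0.12 + 0.88(1 − r)]:
- r = 0.30: 0.42 / 0.736 = 57%
- r = 0.50: 0.30 / 0.56 = 54%
- r = 0.70: 0.18 / 0.384 = 47%

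An 11- to 21-point gap appears with no true effect.

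**Ever-response arithmetic.** With a = S(3) = 0.60^(1/8) = 0.938, P(ever respond) = q·a·[1 − (1 − q)^8 × 0.60] / [1 − (1 − q)a]. For q = 0.20 this is 0.676. Retention is 0.60 × 0.832 / 0.676 = 74% in ever-responders and 0.60 × 0.168 / 0.324 = 31% in never-responders. For q = 0.05 it is 78% versus 54%.

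**Simulated null** (1,000 runs per setting, n = 370, 60% retention; ranges are over q):

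| Grouping | Apparent hazard ratio | Log-rank false positives |
|---|---|---|
| Ever versus never responder, from first infusion | 0.22–0.38 | about 100% |
| Response by month 12, earlier stoppers as non-responders | 0.28–0.41 | 91–100% |
| Response by month 6, earlier stoppers as non-responders | 0.61–0.67 | 16–78% |
| Response by month 6, earlier stoppers excluded | 0.97–0.99 | 4–7% |
| Landmark at month 6 | 0.97–0.99 | 4.1–6.6% |
| Landmark at month 12 | 0.97–0.99 | 5.7–6.3% |

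Here q = 0.05 to 0.20 means that 1 − (1 − q)² = 10% to 36% respond by month 6. A separate null run with 30% to 70% responding at month 6 and the same rule gave 65% to 100% false positives. The simulation standard error near 5% is √(0.05 × 0.95 / 1,000) = 0.7 points.

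**Other sizes.** For the pooled first-line group (n = 755, 70% retention, within the 65–75% of Section 4.3.1), false positives are about 100% (ever-response), 99–100% (month 12) and 23–89% (month 6), against 4.1–5.8% with a landmark. With n = 100 and 60% retention they are 64–100% (ever-response) and 4.5–23% (month 6). A small country's test will often miss the artefact, but the curves are displaced by the same amount.

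**The case against.** The strongest reply is that the biased analysis is inferred. Section 4.2 does not say that time runs from first infusion, does not fix when response is classified, and does not say that early stoppers count as non-responders. If they are excluded the bias disappears. The only example given, the number of previous TNF blockers failed, is known at baseline, and DAS28 and HAQ-DI also have baseline values. Section 4.1.1 defers detail on the derived outcomes to a separate analysis plan, and the log-rank, Cox and tree analyses are exploratory.

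Most of this stands and limits the point. It does not remove it. The protocol does fix a plain log-rank test on subgroups that include outcomes knowable only after baseline, it wants on-treatment outcomes as determinants, and its data set excludes nobody for stopping early. The per-determinant Kaplan-Meier text also falls back on the last available data when the 24-month value is missing. On one reading this classifies early stoppers by their status when they stopped, which again ties group to time on drug.

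A reader might go further and infer four things that the protocol does not support:
- That responders are event-free throughout. They are event-free only until classified; under the assumptions above, 32% of month-6 responders stop by month 24.
- That the Cox and tree models enter response as a fixed baseline covariate. The coding is not stated, and a time-dependent covariate fits the wording.
- That any association found would be false. The Introduction gives lack of efficacy as a reason for stopping TNF blockers, so a real association that is inflated is at least as likely as one created from nothing.
- That the test is meant to be run at alpha = 0.95. Beside the 95% confidence intervals in Section 4.2, this is a slip for 5%.

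**Conclusion.** The point holds as a moderate one. As written, the plan permits, and on its natural reading leads to, a guarantee-time comparison whenever the grouping is on-treatment response. The false-positive range of about 16% to 100% at n = 370 rests on time counted from first infusion, on ever-response or early stoppers counted as non-responders, and on assumed response rates.

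The risk extends to the per-determinant retention rates and Kaplan-Meier curves for secondary objectives 1 and 2 when the determinant is an on-treatment outcome. Comparisons by prior TNF failures or by baseline DAS28 or HAQ-DI are unaffected, as are the primary retention estimate and its precision. The documents do not support the stronger reading that the stated method must produce false determinants, because the classification rule that decides this is not written.

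**What to change.** In Section 4.2:
- Keep Kaplan-Meier curves and log-rank tests from first infusion for characteristics known at baseline.
- For EULAR response, low disease activity, remission, HAQ response, onset and durability, use either a landmark analysis (patients still on abatacept at month 6 or 12, grouped by status at that time, time counted from the landmark) or a Cox model with response as a time-dependent covariate. Apply the same rule to the per-determinant retention estimates.
- Replace the stated test level with a two-sided 5% significance level.

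The cost is wording and modest programming, with no new data. The landmark drops patients who stop before it: with 370 patients and 60% retention, about 44 at month 6 (370 × 0.12) and 83 at month 12 (370 × 0.225). Its result applies only to patients still treated at the landmark, so early stoppers should be described separately.
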